### *Eligibility*

Potential participants will be eligible if they report:

- 1) Male sex at birth and current male identity
- 2) Age 16 years and above
- 3) At least 1 CAS act with an HIV-positive or status-unknown male partner in the prior month
- 4) At least 1 heavy drinking day in the prior month
- 5) Own a mobile device (e.g., smartphone, tablet, laptop)
- 6) Planned residence in Romania for the duration of study participation (12 months)
- 7) Not currently using HIV pre-exposure prophylaxis (PrEP)
- 8) Confirmed to be HIV-negative upon testing at baseline

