### *Baseline (BL), 4-, 8-, and 12-month Assessments*

The project coordinator will send a link to the BL survey to all HIV-negative participants, and tell them that they will be contacted by their counselor after submitting the survey. The quarterly self-administered mobile assessments are identical, take 45 minutes to complete, have been validated by the Romanian pilot gay and bisexual men participants, and assess: 1) sexual

behavior (e.g., number of CAS acts; number and types of partners; sex under the influence) and 2) past-3-month alcohol use; 3) depressive symptoms; 4) HIV/STI testing and other healthcare access (e.g., annual exams; mental health) patterns; 5) hypothesized mediators of intervention efficacy, including IMB model components (e.g., HIV-risk-related information, motivation, behavioral skills) and minority stress (e.g., outness, internalized homonegativity, collective self-worth); and 6) demographics and psychosocial risk contexts, including intimate partner violence. Third, during the follow-up phase (mos 8-55), we will assess at 4, 8, and 12-mos post-baseline, in the same web-based fashion as at baseline, the primary outcome of CAS with male partners, and secondary outcomes of alcohol abuse, depression, anxiety, and psychosocial mechanisms rooted in the Information-Motivation-Behavioral Skills (IMB) model (e.g., HIV/STI knowledge, condom use self-efficacy) and minority stress theory (e.g., identity concealment, stigma consciousness).

We hypothesize that 1) compared to gay and bisexual men in the education attention control arm, those randomized to the Comunica arm will report significant reductions in CAS acts, depression symptoms, and anxiety symptoms across the 12-month follow-up, 2) IMB and minority stress mechanisms will statistically mediate intervention efficacy, and 3) compared to the control condition, the Comunica intervention will prove cost-effective in terms of reducing depression, anxiety, and alcohol abuse.

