HIV-risk behavior	HIV-transmission-risk behavior (1°)	Condomless anal sex acts with HIV-positive or unknown-status partners outside of the context of one’s own adherent PrEP use or only with a primary partner that has adherent PrEP use or has undetectable viral load. This is measured with an online self-administered Timeline Follow-Back (TLFB) instrument. The TLFB yields past-30-day incidence of HIV risk behavior in terms of type of sexual behavior, condom use, partner(s) HIV status, self and partner adherent PrEP use (at least 4 days per week), sex while using drugs or alcohol, and number of sexual partners. HIV risk behavior acts as defined above will be measured as the pooled number (count) over 30 days prior to the 4-, 8-, and 12-month follow-up visits. A primary supportive analysis of this outcome will assess the above as any such behavior (binary) during the 30 days prior to the 4-, 8- and 12-month follow-up visits.
Mental health and substance use	Depression (2°)	Center for Epidemiologic Studies Depression Scale (CES-D) (continuous) at 4-, 8-, and 12-month follow-up visits and using cutoff ≥ 16 (binary) at 4-, 8-, and 12-month follow-up
	Anxiety (2°)	Beck Anxiety Inventory (BAI) (continuous) at 4-, 8-, and 12-month follow-up visits and using cutoff ≥ 16 (binary) at 4-, 8-, and 12-month follow-up

	Heavy alcohol use (2°)	Alcohol Use Disorders Identification Test (AUDIT-C) (continuous) at 4-, 8-, and 12-month follow-up and using cutoff ≥ 4 (binary) at 4-, 8-, and 12-month follow-up; Percentage of TLFB-Heavy Drinking Days in the previous 30 days
	Suicidality (2°)	Suicidal Ideation Attributes Scale (SIDAS) (continuous) at 4-, 8-, and 12-month follow-up and using cutoffs ≥ 21 (binary) at 4-, 8-, and 12-month follow-up

Table 2. Exploratory Outcome Measures

Domain	Measure	Source, Frequency, and Sample
HIV-risk behavior	HIV/STI testing	HIV/STI testing (any/none) (besides study-administered testing) over 12 months
	HIV and STI diagnosis	HIV and STI self-reported testing (gonorrhea; chlamydia; syphilis) (besides study-administered testing) over 12 months

Sample size

The primary and secondary outcome measures are summarized in Table 1.

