The Comunică study originally proposed to recruit 326 subjects. This was based on calculations that the study would have 80% power to detect effect sizes ranging from 0.25 to 0.27 if the study attained 80% retention of the study subjects. However, recruitment was slower than planned (due to the COVID-19 pandemic and likely other factors), although retention was better than the 80% estimated.

Therefore, as we approached the end of recruitment for the Comunică study, three factors that were not available when we wrote the proposal transpired: i) While 303 participants were finally enrolled, we had re-estimated that we would likely only be able to recruit 288 subjects by 31 December 2022 (our date of termination of recruitment) and based power re-estimation on this number. ii) The overall participation rate for attending all three post-intervention visits was 86% (with a high proportion of the remaining sample completing 2 post-interventions assessments). iii) From preliminary analysis of our data, we had normative distributions of the study outcomes that could be used in establishing a study design and metrics for powering the primary outcome. To that end, we re-estimated the study power as described below and this new estimate was approved by the Data Safety and Monitoring Board (DSMB).

In the original proposal, a repeated measures mixed linear model (or generalized estimation equation) using all 4 study visits (Baseline, and 4-, 8-, and 12-month follow-ups) was planned. However, the distribution of our primary outcomes (HIV-transmission-risk behavior) based on the data we now had near the end of the study was problematic for fitting this type of model, which is based on a central limit theorem assumption that may not manifest. Namely, there were two issues to consider: 1) at each follow up visit, over 50% of participants manifest no HIV-transmission-risk behavior creating a large point mass at the lower limit of 0. 2) On the other end, the distribution of HIV-transmission-risk behavior acts was very skewed with numbers of acts greater than 50 leading to skewness much > 3 , which again contradicts normality-based methods.

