Importantly for power estimation, the correlation of baseline and the average 12-month HIV-transmission-risk behavior acts was 0.37, which means that after adjustment for the pre-intervention behavior, the standard deviation of the post-intervention behavior would be the square root of $(1-0.37^2) = 0.93$ that of the unadjusted outcome. Based on this and with 288 subjects, 86% of whom participated in all 3 visits as we have been observing will happen (or conservatively 123 in each treatment arm), there is 80% power to detect an effect size of 0.33, slightly greater than our originally estimated effect size of 0.25-0.27 and at the upper end of the range of effect sizes found for behavioral interventions addressing multiple health outcomes among sexual minority men (Pantalone et al., 2020). We believe that 0.33 represents a plausible effect size to detect in this trial given the strong distinction between the two intervention conditions, with one involving an active therapist-guided intervention and the other consisting of self-guided psychoeducation only. The standard deviation of the (Winsorized)

averaged outcome over 12 months per-assessment HIV-transmission-risk behavior acts was 3.46 acts. Multiplying this standard deviation by the effect size of 0.33 gives 1.14 HIV-transmission-risk behavior acts. This means that the study will have 80% power to detect an overall mean reduction of 1.14 HIV-transmission-risk behavior acts in the prior 30 days per assessment period in the intervention compared to the control condition.

It should be noted that our final analysis will most likely incorporate the partial information from men with only 1 and 2 post-intervention follow-up visits through imputations or more exactly adjustment of the partial information for number of trimesters reported. If so, this would increase power, by a very modest amount.

DRAFT ANALYTIC PLAN FOR COMUNICĂ STUDY

1. Overview

The analysis of the primary and secondary outcomes will use intent-to-treat with participants analyzed according to their original treatment assignment. SAS 9.4, SPSS 26.0, Stata and/or R software will be used for all analyses.

2. Comparability of Treatment Groups

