We will also look at the following binary outcomes: HIV-transmission-risk behavior > 0 , CES-D ≥ 16 , SIDAS ≥ 21 , SIDAS ≥ 0 , AUDIT-C ≥ 4 in repeated measures model using the post-baseline visit and post intervention visits at 4-, 8-, and 12-month follow-ups. Repeated measures generalized estimation equations will be fit about individual as the cluster using a logit link. The visit number (i.e., 4-, 8-, and 12-months vs. vs. baseline) and treatment arm assignment will be included as main effects, as will the baseline preintervention level of the outcome being modeled. In sensitivity analyses, this will be repeated including all baseline covariates that are statistically associated ($p < 0.05$) with the outcome using Stepwise selection ($p < 0.05$ to enter $p \geq 0.10$ to leave) into the above-described models. The intervention effect will be quantified by Odds Ratios with 95% confidence intervals.

We will also use exact tests to compare treatment arms for having been ever diagnosed during the single timepoint 12-month study follow up with HIV, syphilis, chlamydia, and gonorrhea.

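### The any-versus-none risk-behavior model in SAP 4-C adjusts for a baseline yes/no that entry makes nearly constant; the baseline act count would recover more precision

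*SAP*

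**What the plan says.** SAP Table 1 makes any-versus-none risk behavior in the prior 30 days the primary supportive analysis of the primary outcome. Section 4-C fits it by logit GEE clustered on the man. Visit and arm are main effects, "as will the baseline preintervention level of the outcome being modeled". For this outcome, the plain reading of that phrase is the baseline yes/no. Stepwise baseline covariates enter only as a sensitivity analysis, and the act count is not named among them.

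The Protocol (Eligibility) admits men who report "At least 1 CAS act with an HIV-positive or status-unknown male partner in the prior month" and excludes current PrEP users. The outcome definition in SAP Table 1 is narrower than the entry criterion. It also leaves out acts under the man's own adherent PrEP use, "or only with a primary partner that has adherent PrEP use or has undetectable viral load".

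Elsewhere the plan uses baseline behavior as a quantity. It enters the negative binomial model (section 3), the ANCOVA sensitivity model (Other Sensitivity Analyses) and the power model (Sample size). The Sample size section reports that "the correlation of baseline and the average 12-month HIV-transmission-risk behavior acts was 0.37".

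**The concern.** The trial selects men on nearly the same event that the binary model then uses as its baseline covariate. A man who met the entry criterion should usually score yes at baseline. The own-PrEP exemption is largely closed by the PrEP exclusion. Two routes to a baseline zero remain: acts only with a protected primary partner, and a shift in the 30-day window between screening and the baseline survey.

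A covariate that is 1 for nearly everyone duplicates the intercept. The analysis would be described as baseline-adjusted while behaving almost like an unadjusted one. If every man is 1, software will drop the term or fail to estimate it. What does vary between men at baseline is the number of acts, and the main 4-C model does not name it. Precision in the supportive analysis is at stake, together with a possible estimation problem that the SAP does not anticipate.

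**Working it through.** **1. The plan's own power figure, and what it owes to the baseline count.** Inputs from the SAP (Sample size): 123 men per arm, effect size 0.33, correlation 0.37, two-sided 0.05.

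- Residual SD factor: √(1 − 0.37²) = 0.929.
- Adjusted: SE = 0.929 × √(2/123) = 0.1185; 0.33/0.1185 = 2.786; power = Φ(2.786 − 1.96) = 79.5%. This reproduces the stated 80%.
- Unadjusted: SE = √(2/123) = 0.1275; 0.33/0.1275 = 2.588; power = Φ(2.588 − 1.96) = 73.5%.

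The baseline count explains 0.37² = 13.7% of the variance of the averaged count and is worth 6 points of power there. The SAP gives no power figure for the binary analysis.

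**2. What a nearly constant yes/no can explain.** Let q be the share of men with a baseline zero, and Δ the difference in follow-up risk between baseline-yes and baseline-no men. Both are assumptions, since the documents give neither. With follow-up prevalence near one half, the share of variance explained is about q(1 − q)Δ²/0.25.

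- q = 1%, Δ = 0.20: 0.0099 × 0.04/0.25 = 0.2%.
- q = 3%, Δ = 0.40: 0.0291 × 0.16/0.25 = 1.9%.
- q = 10%, Δ = 0.20 to 0.40: 0.09 × 0.04/0.25 = 1.4%, to 0.09 × 0.16/0.25 = 5.8%.
- q = 0: nothing, and the term is collinear with the intercept.

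**3. Simulation of the binary model.** This used a logit GEE with working independence and robust standard errors, on 246 men (2 × 123), three post-baseline visits and a two-sided 0.05 test, with 4,000 runs per setting. It was calibrated to 53% zeros per visit (the SAP says over 50%) and 24% zeros at all three visits (SAP). The conditional arm log-odds ratio was set at −0.62, chosen to give about 75% power unadjusted. Baseline zeros were given to the men with the lowest latent baseline level. The assumed correlation of log(1 + baseline count) with the share of visits with any act was about 0.37.

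| Assumed baseline zeros | Power: none / yes-no / log count | Efficiency gain over none: yes-no / log count |
|---|---|---|
| 0% | 75.1 / 75.1 / 80.6% | 0 / 14.8% |
| 3% | 75.6 / 75.8 / 81.2% | 1.4 / 15.2% |
| 10% | 75.0 / 76.6 / 81.4% | 4.0 / 15.7% |
| 20% | 74.0 / 77.2 / 80.8% | 7.0 / 15.9% |

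Efficiency is the squared ratio of mean |z|. In the first row this is (2.808/2.621)² = 1.148 for the count. In that row the yes/no term could not be estimated in any of the 4,000 runs, so its power is that of the unadjusted model. The Monte Carlo error of each power is √(0.75 × 0.25/4000) = 0.7 points, so comparisons should be read within rows. The count beats the yes/no term by 5.5, 5.4, 4.8 and 3.6 points.

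**4. Weaker correlation.** At an assumed correlation of about 0.20, the yes/no term gains 0, 0.6, 1.2 and 1.8% at the same four shares. The count gains 3.8, 3.9, 4.2 and 3.9%.

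**5. Change of estimand.** With no baseline zeros, the mean fitted odds ratio was 0.619 without baseline and 0.599 with the log count. Adjusting for the count makes the odds ratio conditional on it, which slightly changes the quantity estimated.

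**The case against.** The strongest reply is that the documents never give the share of men with a baseline zero. The Protocol (Baseline, 4-, 8-, and 12-month Assessments) says "The project coordinator will send a link to the BL survey to all HIV-negative participants", so the survey follows the HIV test by an unstated interval and its 30-day window may differ from that at screening. Status over 30 days can also change, since "at each follow up visit, over 50% of participants manifest no HIV-transmission-risk behavior". This stands: near-constancy is an inference from the entry criteria. It limits the size of the problem, but the count still did better at every share tried.

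The word level leaves some room to read the baseline count into 4-C. That is the less natural reading when the outcome being modeled is a yes/no, and the remedy is still to name the covariate.

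A reader might infer more than the documents support:

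- **That the baseline term does nothing.** This is exact only with no baseline zeros. At 10 to 20% zeros the term gains 4 to 7% efficiency in the simulation.
- **That the baseline count goes unused in the trial.** It does not. The primary, ANCOVA and power models all use baseline behavior, and the stepwise sensitivity model in 4-C could admit the count. The gap is confined to the main 4-C model.
- **That the model cannot be fitted.** Section 4-C codes visits against baseline, which raises the question of whether baseline is also an outcome row. If it is, the visit terms approach separation when that row is nearly all ones, and the fit may be unstable under an exchangeable working correlation. The documents support nothing stronger.
- **That the same applies to the other binary outcomes in 4-C.** The argument rests on the entry criterion for sexual behavior. It does not carry over to those cutoffs, and nothing was computed for them.

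Finally, this is a supportive analysis to which the plan attaches no success rule.

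**Conclusion.** The point holds as a matter of precision and specification. On the plain reading, the main 4-C model adjusts the supportive analysis of the primary outcome for a variable that entry pushes toward a single value. That variable recovers little precision and cannot be estimated if every man is 1. The randomized comparison is not biased.

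Using the baseline count is worth about 15% efficiency over no adjustment if its correlation with any-act status is near 0.37, and about 4% if it is near 0.20. At the higher value this is about 3.6 to 5.5 power points more than the yes/no term. The figures are illustrative. The SAP reports 0.37 for the averaged count, so carrying it to the binary outcome is an assumption, as are the baseline-zero shares and the effect size. The direction did not depend on those shares, and the change is worth making because it uses data already collected.

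**What to change.** In SAP 4-C, for any HIV-transmission-risk behavior only:

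- Fit the logit GEE to the 4-, 8- and 12-month rows, so that baseline is a covariate and not an outcome row.
- Use log(1 + baseline 30-day act count) as the baseline covariate in place of the baseline yes/no, counting acts by the SAP Table 1 definition.
- Report the number of men with a baseline zero.
- State that the odds ratio is conditional on the baseline count.

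This costs a sentence or two in a plan still headed as a draft. It needs no new data. The one thing given up is that the odds ratio is no longer directly comparable with an unadjusted one.

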## BACKGROUND

### *Study Purpose and Rationale*

This research is designed to remedy unaddressed and interlocking HIV-prevention and mental health needs among gay, bisexual, and other men who have sex with men (GBMSM) in the Central Eastern European country of Romania, and their underpinning stigma-related mechanisms. Rampant stigma contributes to the increasing prevalence of HIV among Romanian GBMSM (from under 10% in 2009 to close to 20% in 2014, by best available estimates) and keeps GBMSM out-of-reach of HIV prevention services. The team's mHealth pilot intervention (titled "Comunica: Despre Mine. Despre Noi." [COMUNICA] translated as "About Me. About Us."), which reduced US and Romanian GBMSM's risk for HIV infection while also reducing depression and alcohol abuse in initial pre-post trials, is now ready for testing in a randomized controlled trial with a large national sample in the current study. The Comunica intervention entails eight 60-minute live chat sessions delivered by trained counselors on our mobile study platform using motivational interviewing (MI) and cognitive-behavioral skills training (CBST).

First, during pre-trial (months 1-5), in collaboration with a community advisory board consisting of GBMSM community members, GBMSM-affirmative physical and mental health providers, and a technical developer, the team fine-tuned the Comunica intervention based on pilot findings and evaluation interviews, and expand the original Comunica education materials for an education attention condition that will serve as a control arm.

Second, during the intervention phase (months 6-45), the team will recruit, screen, assess, and randomize GBMSM at risk for HIV infection and alcohol abuse to either the Comunica intervention (n=163) or education attention condition (n=163). The conditions are content matched, and both are hosted on the study platform. While Comunica will consist of eight weekly mHealth live chat sessions, the education attention control condition will consist of eight self-administered educational modules.

Third, during the follow-up phase (months 8-55), the team will assess at 4, 8, and 12 months post-baseline, in a mobile fashion identical to the baseline, the primary outcome of condomless anal sex (CAS) with male partners, secondary outcomes of alcohol abuse, depression, and anxiety, and psychosocial mechanisms rooted in the Information-Motivation-Behavioral Skills (IMB)

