**Building Mobile HIV Prevention and Mental Health Support in Low-resource
Settings**

NCT #: NCT03912753

July 8, 2024

Statistical Analysis Plan

Introduction

The current study aims to test the efficacy of Comunică, a motivational interviewing intervention also informed by minority stress theory, to reduce HIV-transmission-risk behavior in a randomized controlled trial among Romanian gay and bisexual men (GBM). In this study, the primary outcome involves HIV-transmission-risk behavior. Secondary outcomes include depression, anxiety, heavy alcohol use, and suicidality. Exploratory outcomes include HIV and STI (chlamydia, gonorrhea, syphilis) diagnosis and HIV/STI testing patterns. The control condition, referred to as “educational attention control (EAC)” consists of eight educational modules that present information regarding GBM’s identity development, HIV/STI prevention, heavy alcohol use and its associations with HIV-transmission-risk behavior, sexual health communication, and the importance of social support. This EAC was created in consultation with Romanian GBM community members and advocates.

Study Design

In this RCT, Comunică is compared to EAC to examine relative change in: (a) the primary outcome, HIV-transmission-risk behavior defined as: frequency of condomless anal sex acts with HIV-positive or unknown-status partners outside of the context of one’s own adherent PrEP use or only with a primary partner that has adherent PrEP use or has undetectable viral load and (b) secondary outcomes: depression, anxiety, heavy alcohol use, and suicidality. Sessions for both conditions are to be completed over the course of four months. Outcomes are measured by self-report at pre-intervention (baseline), and at 4-, 8-, and 12-month follow-ups. At baseline and 12-month follow-up, all participants also self-administer at-home rapid testing for HIV and syphilis, and self-collect sampling (urethral, pharyngeal, rectal) for chlamydia and gonorrhea, which are sent to a laboratory for analyses.

Table 1. Primary and Secondary Outcome Measures

Domain	Measure (1°, 2°)	Source, Frequency, and Sample

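### The 12-month arm comparison of syphilis, chlamydia and gonorrhea does not use the baseline test results, so positivity carried over from entry can dilute it

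*SAP*

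**What the plan says.** - **Testing.** SAP, Study Design: "At baseline and 12-month follow-up, all participants also self-administer at-home rapid testing for HIV and syphilis". At the same two visits participants "self-collect sampling (urethral, pharyngeal, rectal) for chlamydia and gonorrhea", with laboratory analysis. Status for all four infections is therefore collected at both ends of the trial.
- **Entry.** The only infection-related criterion in the protocol's Eligibility section is "Confirmed to be HIV-negative upon testing at baseline". Syphilis, chlamydia and gonorrhea are not exclusions. The protocol's Study Purpose and Rationale puts assessment ahead of allocation: "the team will recruit, screen, assess, and randomize".
- **Comparison.** SAP section 4-C plans "exact tests to compare treatment arms for having been ever diagnosed during the single timepoint 12-month study follow up" with each infection. It states no restriction to men negative at baseline, no stratification and no definition of a new infection.
- **Contrast within the same section.** For the other binary outcomes, the GEE models include visit and arm, "as will the baseline preintervention level of the outcome being modeled".
- **Outcome definition.** SAP Table 2, which lists exploratory outcomes, describes "HIV and STI self-reported testing (gonorrhea; chlamydia; syphilis) (besides study-administered testing) over 12 months".

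**The concern.** A plain exact test on a two-by-two table takes no covariate, so baseline status can enter only by restricting or stratifying, and section 4-C does neither. For HIV this does no harm, because everyone is negative at entry and a positive at 12 months is new. For the other three infections, a positive 12-month study test can be a new infection or positivity already present at randomisation. Syphilis could be the clearest case if the rapid test detects antibody, but the documents do not say what it detects.

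The intervention cannot prevent an infection that predates it. Carried-over positives add about equally to both arms and shrink the relative difference. The primary outcome is self-reported, so readers will look to the infection results for supporting evidence. It is therefore worth knowing whether they describe new infections or 12-month positivity. Leaving the at-risk set undefined also leaves it open to choice once results are known.

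**Working it through.** **Plan's own figures.** The documents give no rate, power or alpha for the infection comparison. I take only the arm size, 123, from the SAP's Sample size section: 288 × 0.86 = 247.7, or 123.8 per arm. As a check on that number, the primary-outcome calculation (effect 0.33, SD factor √(1 − 0.37²) = 0.929, two-sided 0.05) gives 79.5% power at 123 per arm, against 80% stated.

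**Assumptions, none of them in the documents.** p = share positive at baseline; s = share of those still positive at 12 months; i = risk of new infection over 12 months. The true risk ratio (RR) is 0.50, so the treated arm has i/2. Baseline-positive men who clear the infection face the same risk i. The 12-month study test is the source of diagnosis.

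**Apparent risk ratio**

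12-month positivity = (1 − p)·i + p·[s + (1 − s)·i] = i + p·s·(1 − i)

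| p | s | control i | control positivity | treated positivity | apparent RR |
|---|---|---|---|---|---|
| any | 0 | any | i | i/2 | 0.50 |
| 10% | 10% | 10% | 0.10 + 0.01 × 0.90 = 0.109 | 0.05 + 0.01 × 0.95 = 0.0595 | 0.55 |
| 5% | 50% | 10% | 0.10 + 0.025 × 0.90 = 0.1225 | 0.05 + 0.025 × 0.95 = 0.0738 | 0.60 |
| 10% | 100% | 5% | 0.05 + 0.10 × 0.95 = 0.145 | 0.025 + 0.10 × 0.975 = 0.1225 | 0.84 |
| 15% | 100% | 5% | 0.05 + 0.15 × 0.95 = 0.1925 | 0.025 + 0.15 × 0.975 = 0.1713 | 0.89 |

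Dilution grows with p and s and shrinks with i, so the first and last rows bound the range for p 5-15%, s 0-100% and i 5-10%. The share of control positives that predate entry, p·s divided by control positivity, runs from 0 to 0.15/0.1925 = 78%.

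**Power.** Two-sided Fisher test at an assumed 0.05, 123 per arm, p = 10%, true incidence 20% against 10%. Restriction leaves 123 × 0.90 ≈ 111 per arm.

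| s | all men, control vs treated | RR | power, all men | power, baseline-negative men (RR 0.50) |
|---|---|---|---|---|
| 0 | 20.0% vs 10.0% | 0.50 | 53% | 49% |
| 25% | 22.0% vs 12.3% | 0.56 | 46% | 49% |
| 50% | 24.0% vs 14.5% | 0.60 | 41% | 49% |
| 100% | 28.0% vs 19.0% | 0.68 | 33% | 49% |

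At incidence 10% against 5% with the same p, all-men power falls from 23% (s = 0) to 12% (s = 100%), against 22% with restriction.

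**False positives.** With no true difference, the all-men Fisher test rejects in 2.9% to 3.8% of trials across the scenarios run (p 0-20%, s 0-100%, control incidence 10% or 20%). Chance imbalance in baseline positives is already part of that calculation.

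**The case against.** **The SAP is silent, not wrong.** It nowhere says that infections present at entry are counted, and a diagnosis during follow-up could mean post-baseline diagnoses only. The first part stands. The second does not settle the matter, because a positive 12-month test is found during follow-up whether the infection is old or new.

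**Table 2 may govern.** If the outcome is self-reported and excludes study tests, persistent positivity on the 12-month study test cannot enter it. This stands, and it makes the point conditional on the data source. Section 4-C's single 12-month timepoint fits the study testing in Study Design better than it fits Table 2, but the SAP does not resolve the conflict.

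**Persistence may be low.** Nothing in the documents supports high persistence, least of all for chlamydia and gonorrhea. This stands. At 10% persistence the distortion is small (0.50 becomes 0.55), and at zero there is none.

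**All randomised men is a legitimate comparison.** It is valid as a comparison of 12-month positivity, and restriction drops genuine reinfections among baseline-positive men. This stands too. It is a reason to keep the all-men analysis as a sensitivity analysis and to offer stratification.

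**The outcome is exploratory.** That is correct, and it limits what is at stake.

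**Conclusion.** The point holds in a conditional form. If the 12-month study test supplies the diagnosis, section 4-C counts any syphilis, chlamydia or gonorrhea positivity carried over from entry as an outcome, although the baseline results needed to prevent this are collected. Under the assumed ranges a true risk ratio of 0.50 appears as 0.50 to 0.89. Where in that range it falls depends on prevalence and persistence, which the documents do not give.

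A reader might infer more, and the documents do not support it:

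- **That the plan deliberately keeps old infections as outcomes.** It states no rule either way.
- **That this would hide a real effect.** It attenuates the effect. Power for a halving of risk is modest in any case: at 10% prevalence, about 49% with restriction at 20% against 10% incidence, and 22% at 10% against 5%.
- **That an imbalance in baseline positives would manufacture a difference.** The test's false-positive rate stays below 5%.
- **That the trial's biological evidence as a whole is compromised.** HIV is unaffected, and the SAP does not present the infection tests as validation of the primary outcome.

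The primary and secondary conclusions do not depend on this analysis. The change is still worth making, because it is cheap and decides what the infection result means.

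**What to change.** In SAP section 4-C, for each of syphilis, chlamydia and gonorrhea:

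1. State the data source and reconcile section 4-C with Table 2.
2. Define a new infection for that organism.
3. Make the arm comparison among men negative for that infection on the baseline study test, or use an exact test stratified by baseline result.
4. Show baseline-positive men separately by arm, and keep the all-men comparison as a sensitivity analysis.

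HIV needs no change to its at-risk set. The choice should be fixed before infection results are tabulated by arm.

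The cost is SAP wording, since the baseline tests are already part of the study. Restriction loses reinfections among baseline-positive men and, if nothing carries over, a little power: about 53% to 49% at 20% against 10% incidence with 10% prevalence. Stratification keeps those men in the analysis, although within the baseline-positive stratum a persistent positive still cannot be told from a reinfection.
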